Summary statistics will be presented for both groups. Continuous variables will be presented in terms of mean values or medians with SDs and IQRs, respectively. Categorical variables will be presented with relative frequencies in percent.

The results from the statistical analysis will be considered to support a claim of non-inferiority if the upper limit of a one-sided 97.5% CI (or equivalently a 95% two-sided CI) excludes a difference in the primary endpoint in favor of the irrigation group of more than 7.5%. The center stratification of the randomization will be accounted for in the calculation of the CI.

Exploratory analyses of secondary and other binary endpoints will be performed using the χ^2 test or logistic regression analysis. Continuous outcomes will be analyzed using regression Student's t-test, analysis of covariance or regression models.

Potential effect modifiers will be analyzed by including interaction terms in statistical models for the following subgroups:

- patient age (<70 years, \geq 70 years)
- GCS score at baseline (9–12, 13–14, 15)
- history of head trauma (<4 weeks, \geq 4 weeks, head trauma with unknown timing, no head trauma)
- unilateral versus bilateral CSDH
- use of anticoagulation and/or antiplatelet medication versus none
- preoperative mRS (0–3, 4–5)
- hematoma density (isodense, mixed-density, hypodense)
- hematoma size (width in mm)
- presence of membranes on preoperative imaging (yes, no)

The primary endpoint will be investigated as described above using a CI, which is equivalent to using a non-inferiority test with a one-sided p-value of 0.025 (or a two-sided of 0.05). The between-group comparison of 6-month mortality and mRS 4–6 differences will be compared using 85% and 95% CIs (as outlined in more detail in the BDI). The statistical testing of other endpoints will also be performed using a two-sided significance level of 0.05.

STATA (Statistics/Data analysis, SE v15.1, StataCorp LLC, [name]) will be used for analyses.

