 [name] (Jun 27, 2023 07:13 GMT+3) [name] (SCM, trial PI)

 Jun 27, 2023
 [name] (Jun 27, 2023 23:06 GMT+3) [name] (SCM, BDI committee co-chair)

[figure not shown]
 Jun 27, 2023
 [name] (Jun 27, 2023 10:56 GMT+3) [name] (SCM, BDI committee chair)

*SCM = Steering Committee Member of the FINISH trial

4. Blinded data interpretation (BDI)

The data will be interpreted according to a blinded data interpretation scheme we have published and described in detail previously [9]. In brief, the FINISH statistician (TC) will carry out the statistical analyses, blinded to the group assignment, and presents the data as Group A and Group B. The FINISH Blinded Data Interpretation committee will then contemplate the blinded results until a consensus on the interpretation is reached. Once the Blinded Data Interpretation committee reaches a consensus, the data will be unblinded and no changes are made to the interpretation of the results.

The sequence of events to take place in the upcoming ‘blinded data interpretation meeting’ is outlined in the flow chart below:

The final BDI plan was approved by:

Jun 27, 2023
[name] (Jun 27, 2023 07:13 GMT+3)
[name] (trial PI)

Jun 27, 2023
[name] (Jun 27, 2023 00:01 GMT+3)
[name] (local PI, SCM)

Jun 27, 2023
[name] (Jun 27, 2023 08:43 GMT+3)
[name] (local PI, SCM)

Jun 28, 2023
[name] (Jun 28, 2023 15:02 GMT+3)
[name] (local PI, SCM)

Jun 27, 2023
[name] (Jun 27, 2023 08:33 GMT+3)
[name] (local PI, SCM)

Jun 27, 2023
[name] (Jun 27, 2023 08:21 GMT+3)
[name] (local PI, SCM)

Jun 27, 2023
[name] (Jun 27, 2023 14:13 GMT+3)
[name] (SCM)

Jun 27, 2023
[name] (Jun 27, 2023 07:55 GMT+3)
[name] (SCM)

Jun 28, 2023
[name] (Jun 28, 2023 10:49 GMT+2)
[name] (trial statistician)

Jun 27, 2023
[name] (Jun 27, 2023 18:40 GMT+2)
[name] (BDI committee member)

Jun 27, 2023
[name] (Jun 27, 2023 09:55 GMT+3)
[name] (SCM, BDI committee member)

Jun 27, 2023
[name] (Jun 27, 2023 23:06 GMT+3)
[name] (SCM, BDI committee co-chair)

Jun 27, 2023
[name] (Jun 27, 2023 10:56 GMT+3)
[name] (SCM, BDI committee chair)

*SCM = Steering Committee Member of the FINISH trial

Minutes of the BDI**[BLINDED VALUES TO BE ADDED BY TRIAL STATISTICIAN PRIOR TO THE BDI MEETING]****Step 1: Analysis of efficacy (primary, non-inferiority analysis)**

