Is no intraoperative irrigation non-inferior to irrigation in preventing symptomatic CSDH recurrence that requires reoperation after burr-hole craniostomy and subdural drainage in patients with CSDH? Based on the data in Table 2 and Figures 2 and 3, we will make an initial (blinded) interpretation on efficacy. Table 1 below describes the baseline characteristics of the study population.

Table 1. Baseline characteristics of the participants randomly assigned to irrigation or no irrigation.

Characteristic	Group A (n=??)	Group B (n=??)
Age – yr		
Female sex – no./total no. (%)		
Medical comorbidities – no./total no. (%)		
Diabetes mellitus		
Cardiac arrhythmia		
Previous cerebrovascular event		
Hypertension		
Ischemic heart disease or peripheral artery disease		
Cardiac valve prosthesis		
Pulmonary embolism or deep vein thrombosis*		
Dementia		
History of head trauma – no./total no. (%)		
Yes		
No		
Unknown		
Preoperative use of antithrombotic medication – no./total no. (%)		
No		
Antiplatelet		
Anticoagulant		
Symptoms at admission – no./total no. (%)		
Gait disturbance or falls		
Hemiparesis		
Speech disturbance		
Cognitive impairment		
Headache		
Seizure		
Other		
GCS at admission – no./total no. (%)		
15		
13–14		
9–12		
mRS at admission – no./total no. (%)		
1–3		
4–5		
Midline shift – mm		
Hematoma laterality† – no./total no. (%)		
Unilateral		
Bilateral		
Hematoma width, mm – mean (sd)		
Unilateral		
Bilateral‡		
Hematoma density§ – no./total no. (%)		
Isodense		
Hypodense		
Mixed density		
Hematoma membranes§ – no./total no. (%)		
Yes		
No		

* within 12-months before admission

† patient may have a hematoma not operated on

‡ sum of left and right hematoma widths

§ presented as individual hematomas

Abbreviations: GCS=Glasgow Coma Scale, mRS=modified Rankin Scale, SD=Standard Deviation, yr=years

[figure not shown]
Figure 1. Trial flow chart.

Table 2. Primary outcome at the primary outcome assessment time point (6 months).

Variable	Group A	Group B	Difference (97.5% CI)	P-value
Intention-to-treat				
Secondary surgery for recurrent CSDH	n=?? ??/n (x%)	n=?? ??/n (??%)	x (x to x)	??
Per-protocol-treated				
Secondary surgery for recurrent CSDH	n=?? ??/n (x%)	n=?? ??/n (??%)	x (x to x)	??

Abbreviations: CSDH=chronic subdural hematoma, CI=confidence interval

Our judgment on the efficacy (non-inferiority) will be based on the location of the whole CI in relation to Δ (non-inferiority margin) [10].

[figure not shown]

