As we will not have knowledge of treatment group assignment (whether Group A or Group B is our “new treatment”, here, no irrigation), and to preserve our blinding, we have deemed it necessary to take both scenarios under consideration, as follows:

[figure not shown]
- We will calculate the treatment group difference assuming first that Group A is the “new treatment” and then that Group B is the “new treatment” (Scenario 1 and Scenario 2).
- We will plot the resulting point estimate with confidence intervals (97.5% CIs) into two separate graphs.
- We will interpret both graphs (Figures 2 and 3).

Figure 2. Scenario 1 – Group A minus Group B.

[EXAMPLE GRAPH BELOW, to be replaced by the actual graph of the FINISH trial data]

**Figure 3.** Scenario 2 – Group B minus Group A.

[EXAMPLE GRAPH BELOW, to be replaced by the actual graph of the FINISH trial data]

Step 2: Initial interpretation of efficacy

Based on the location of the whole CI in relation to Δ (non-inferiority margin), our initial interpretation on the non-inferiority of no irrigation vs. irrigation, is as follows:

Scenario 1 (Figure 2) [INCORRECT OPTION TO BE REMOVED]

1. Among adults with symptomatic chronic subdural hematoma who had undergone burr-hole drainage, Group A was [superior A / non-inferior B, C, D / inferior H] to Group B in preventing reoperations.

OR

2. Among adults with symptomatic chronic subdural hematoma who had undergone burr-hole drainage, the effect of Group A compared to Group B in preventing reoperations was inconclusive [E, F, G].

Scenario 2 (Figure 3) [INCORRECT OPTION TO BE REMOVED]

3. Among adults with symptomatic chronic subdural hematoma who had undergone burr-hole drainage, Group B was [superior A / non-inferior B, C, D / inferior H] to Group A in preventing reoperations.

OR

4. Among adults with symptomatic chronic subdural hematoma who had undergone burr-hole drainage, the effect of Group A compared to Group B in preventing reoperations was inconclusive [E, F, G].

Step 3: Analysis of safety concerns

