			Difference	“Interpretation commitment” from Tables 3 and 4 added if criteria for addition to conclusion is fulfilled.
	Inconclusive	Among adults with symptomatic chronic subdural hematoma who had undergone burr-hole drainage, the effect of intraoperative irrigation compared to no intraoperative irrigation in preventing reoperations was inconclusive .	No difference	There were no relevant differences in mortality or functional outcome between the groups.
			Difference	“Interpretation commitment” from Tables 3 and 4 added if criteria for addition to conclusion is fulfilled.

Step 6: Final interpretation

Our final interpretation of the FINISH trial stands as follows:

[COPY PASTE THE CORRECT INTERPRETATION HERE FROM STEP 5]

Place: [ZOOM-/Teams-meeting]
Time: [Insert date here]

[name]
(BDI committee chair)

[name]
(BDI committee co-chair)

[name]
(trial statistician)

[name]
(BDI committee member)

[name], member
(BDI committee member)

Also present at the meeting:

4. References

1. Tommiska P, [name] R, Schwartz C, Kivisaari R, Luostarinen T, Satopää J, et al. Finnish study of intraoperative irrigation versus drain alone after evacuation of chronic subdural haematoma (FINISH): a study protocol for a multicentre randomised controlled trial. *BMJ Open* [Internet]. 2020 [cited 2020 Aug 21];10. Available from: <https://www.ncbi.nlm.nih.gov/pmc/articles/PMC7311024/>
4. van Swieten JC, Koudstaal PJ, Visser MC, Schouten HJ, van Gijn J. Interobserver agreement for the assessment of handicap in stroke patients. *Stroke*. 1988;19:604–7.

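### The fixed conclusion calls the effect on reoperations inconclusive even when the CI lies wholly above 0 and non-inferiority alone is unresolved

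*SAP*

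**What the plan says.** Section 3.2 rests the non-inferiority claim on the upper confidence limit at the one-sided 97.5% level. The criterion there reads: "or equivalently a 95% two-sided CI) excludes a difference in the primary endpoint in favor of the irrigation group of more than 7.5" (percentage points). Step 1 of the blinded data interpretation, below Table 2, adds: "Our judgment on the efficacy (non-inferiority) will be based on the location of the whole CI in relation to Δ (non-inferiority margin").

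Step 2 assigns letters to CI positions. The options are "superior A / non-inferior B, C, D / inferior H", or else a single shared sentence: "the effect of Group A compared to Group B in preventing reoperations was inconclusive [E, F, G"]. Step 5 has the same four rows, under a column headed as the interpretation based on the primary outcome. Its inconclusive row reads "the effect of intraoperative irrigation compared to no intraoperative irrigation in preventing reoperations was inconclusive".

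Step 6 then instructs: "COPY PASTE THE CORRECT INTERPRETATION HERE FROM STEP 5". Section 4 states that after consensus "the data will be unblinded and no changes are made to the interpretation of the results".

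The CI level is labelled differently in the interpretation steps. Table 2 is headed 97.5% CI, and Step 1 says "We will plot the resulting point estimate with confidence intervals (97.5% CIs) into two separate graphs".

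**The concern.** The sentence answers a different question from the one that is unresolved. If the CI for the excess of reoperations without irrigation includes 7.5, non-inferiority is unresolved. If that same CI lies wholly above 0, the existence and direction of an effect are not unresolved: equality is rejected at the matching two-sided level. The Step 5 sentence nevertheless applies 'inconclusive' to the effect on reoperations and does not mention non-inferiority.

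The scheme is also asymmetric. A difference favouring no irrigation has its own row (superior). A difference of the same size favouring irrigation has none unless the whole CI exceeds the margin.

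Because the sentence is fixed in advance and copied unchanged, a trial that found more reoperations without irrigation would state as its final conclusion only that the effect was inconclusive, beside a table showing a CI that excludes 0.

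**Working it through.** **Inputs from the SAP.** Reoperation rate 9.6%, margin 7.5 points, one-sided alpha 0.025, 80% power and 243 per group (Section 2.9.1); 289 per group and 15.7% non-adherence (Section 2.9.2); two-sided 95% CI (Section 3.2); 97.5% label (Table 2 and Step 1).

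**The plan's own figure.** n = 2 × 0.096 × 0.904 × (1.960 + 0.842)² / 0.075² = 242.2, so 243 per group. This reproduces, and it shows that the design assumes equal rates.

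**Which sentence applies.** Take a CI with lower limit above 0 but below 7.5, and upper limit above 7.5.
- Superior: ruled out, because the difference goes the other way.
- Non-inferior: ruled out by Section 3.2, because the upper limit exceeds 7.5.
- Inferior: judged by the whole CI against the margin, this needs a lower limit above 7.5.
- Inconclusive: the only one left.

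The figure defining A to H is not shown, so this is elimination from the printed text.

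**Worked example.** Risk difference with unstratified Wald CI, d ± z × √[p₁(1−p₁)/n + p₀(1−p₀)/n], n = 289, 28 reoperations with irrigation (9.7%).
- 50 without irrigation (17.3%): d = 7.6, SE = 2.82, 95% CI 2.1 to 13.1. Equality is rejected, yet the sentence is 'inconclusive'.
- At 95%, the pattern runs from 44 events (d = 5.5, CI 0.2 to 10.9) to 66 (d = 13.1, CI 7.2 to 19.1). 'Inferior' starts at 67 (d = 13.5, CI 7.6 to 19.4).

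**The two scenarios on the same data.** Let Group A have 28 and Group B 44 reoperations. Scenario 1 (A minus B) is −5.5, 95% CI −10.9 to −0.2. If 'superior' means a CI below 0, Group A is superior to Group B. Scenario 2 (B minus A) is 0.2 to 10.9, and its option 4 records the effect of A compared with B as inconclusive. A non-inferiority verdict may depend on which arm is new; a statement about the effect of A versus B cannot.

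**How often.** Exact sum over both binomial distributions, 289 per arm, irrigation rate 9.6%, two-sided 95% CI; the true excesses are assumed:

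| True excess (points) | Non-inferior | CI includes 0 and 7.5 | CI above 0, includes 7.5 | Inferior |
|---|---|---|---|---|
| 0 | 86.4% | 11.1% | 2.5% | 0.0% |
| 1 | 73.8% | 20.2% | 5.9% | 0.0% |
| 3 | 41.3% | 37.8% | 20.8% | 0.0% |
| 5 | 15.6% | 38.9% | 45.4% | 0.2% |
| 7.5 | 2.7% | 21.1% | 73.8% | 2.5% |

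At a true excess of 7.5 points, 94.9% of trials are labelled inconclusive (21.1 + 73.8), and 73.8 of those 94.9 points have a CI wholly above 0.

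**Sensitivity of the fourth column**, at excesses 0, 1, 3, 5 and 7.5:
- Two-sided 97.5% CI: 1.3, 3.3, 13.9, 35.0, 65.7%.
- 243 per arm, 95% CI: 2.6, 5.7, 18.5, 39.7, 66.6%.
- Centre-stratified with Mantel-Haenszel weights (assumed centre sizes 101/58/44/43/43 per arm and unequal centre rates averaging 9.6%), 95% CI: 2.7, 6.1, 21.9, 46.6, 74.8%.

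**CI level.** 44 vs 28 events gives 0.2 to 10.9 at 95% but −0.6 to 11.7 at two-sided 97.5%; 45 vs 28 gives 0.5 to 11.3 and −0.3 to 12.1. Trials above 0 at 95% but not at 97.5%: 1.2, 2.6, 6.9, 10.5, 9.4%.

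**ITT and PP.** 200,000 simulated trials, PP a random 244 of 289 per arm (289 × 0.843 = 243.6). Both sets show the pattern in 1.6, 4, 15, 36 and 63%. ITT shows it while the PP CI includes 0 in 0.9, 1.9, 5.6, 9.6 and 9.6%.

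**The case against.** The letters are defined in a figure that is not shown, and it could qualify E, F or G. That stands as a limit on certainty. Any qualifier there would still not reach the Step 5 sentence, which is what gets copied.

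The lead-in to Step 2 presents the interpretation as one on non-inferiority, and for that question 'inconclusive' is correct when the CI includes 7.5. This is the strongest point. It does not rescue Step 5, whose row and column heading do not mention non-inferiority and whose sentence is carried alone into Step 6.

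Readers would still see the difference and CI in Table 2, and the error is conservative: it creates no false non-inferiority claim. Both are true and limit the severity.

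Under the design assumption of equal rates the pattern occurs in only 2.5% of trials, and these are chance findings. Also true; the larger figures need a real excess. But a real excess is the case a non-inferiority trial must be able to report.

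A directional sentence based on ITT could stand beside a PP CI that includes 0, in up to 9.6% of trials at the excesses examined. That is why the PP result should be reported with it.

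**Conclusion.** The concern holds. Followed as written, the plan yields a wrong concluding sentence whenever the CI lies wholly above 0 and includes 7.5. At 289 per arm and 28 irrigation events this covers observed excesses of about 5.5 to 13.1 points at two-sided 95%. Its probability is 2.5% with equal rates and 74% when the true excess equals the margin, while the inferior row is reached in only 2.5% of trials in the latter case.

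These figures rest on a 9.6% irrigation rate, equal arms, an unstratified Wald CI, assumed true excesses and classes inferred without the A to H figure. Stratifying by centre changes little. The pattern remains at two-sided 97.5%, but the unsettled level changes the reading near the boundary.

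The defect is confined to the concluding sentence. The non-inferiority rule, margin, alpha and sample size stand. It should be corrected; confidence is medium because of the missing figure.

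**What to change.** In Steps 2 and 5, make the inconclusive wording refer to non-inferiority and split it by the two-sided 95% CI of Section 3.2:
- CI includes both 0 and 7.5: *non-inferiority was not shown; the difference was inconclusive*.
- CI lies above 0 and includes 7.5: *non-inferiority was not shown; reoperations were more frequent without irrigation (difference, 95% CI)*.

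Base the second statement on the ITT set and give the PP difference and CI beside it. In Step 2, write *more frequent in Group A than in Group B* for Scenario 1 and the reverse for Scenario 2, where option 4 now repeats the Scenario 1 direction. Relabel the 97.5% CI in Table 2 and Step 1 as the two-sided 95% CI.

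Cost: one reworded and one added sentence per scenario in Step 2, one added row in Step 5, and one CI label aligned. The analysis, margin and decision rule do not change.
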